8. STUDY PROCEDURES

Participants will be recruited from multiple sites within travel distance of the John Radcliffe Hospital in Oxford, but the study visits will take place in Oxford (see below).

Each participant will undergo a screening visit, a baseline visit (which can be combined with the screening visit if the test results required for determining eligibility are available) and 3 'on-medication' visits. The screening visit will incorporate an assessment of eligibility and detailed trial explanation, followed by informed consent. They will then have a full medical history and examination, review of medical records, ECG (if one is not available from the previous year) and blood tests (if none available in the previous 3 months). They will then have a baseline study visit, either combined with the screening visit, if the availability of screening results permit, or within 1 month. At the baseline visit, they will undergo a repeat medical history for any events since the screening visit, repeat screening blood tests or ECG (if indicated), a formal cognitive assessment and a physiological assessment. If all eligibility criteria are fulfilled, they will be then assigned a study ID and associated randomisation schedule, followed by provision of allocated medication by the clinical trials pharmacy. Participants will then take each of placebo, sildenafil or cilostazol for 3 weeks each, in random order, at low dose for 1 week followed by titration to full dose for 2 weeks (minimum 11 days). Patients on omeprazole will not increase the dose after one week (due to an interaction with cilostazol). After visits 1 and 2, there will be a minimum of a 1 week washout period prior to starting the new medication. On-treatment visits will include review for SAEs and a repeat core physiological assessment. All participants, up to a maximum of 60, will additionally be invited to undergo an MRI scan at follow ups on placebo and sildenafil (with up to thirty also being scanned on cilostazol).

For participants who are unable to attend an on-treatment study visit once their medication has been started (for example due to the COVID-19 pandemic), then they will be able to restart treatment at the

point of stopping treatment, if still during the titration phase, but otherwise will restart three weeks of treatment from the beginning. The washout period can be prolonged as long as is necessary during the COVID-19 outbreak, before the next treatment phase is started.

Activity / assessment	Screening -21 to 0	Baseline Day 0	Visit 1 Day 28	Visit 2 Day 56	Visit 3 Day 84
Informed Consent	X				
Eligibility Criteria	X				
Demographics	X				
Medical/ History	X	X			
Vital Signs	X		X	X	X
Physical Exam	X		X	X	X
Cognitive Assessment		X			
Pregnancy Test***	(X)	(X)	(X)	(X)	(X)
Laboratory Tests *	X	X	X	X	X
ECG	X				
Randomisation		X			
7 days home BP monitoring twice daily for 1 week		X	X	X	X
Study drug dispensation		X	X	X	
mRS (disability)		X			
NIHSS (stroke severity) only for stroke patients		X			
Drug accountability			X	X	X
Concomitant Medication	X	X	X	X	X
Adverse Events (AE)		X	X	X	X
Pulse wave velocity/ pulse wave analysis		X	X	X	X
Transcranial (TCD) ultrasound scan		X	X	X	X
Beat-to-beat BP monitoring		X	X	X	X
Peripheral Vascular Reactivity		X	X	X	X
MRI assessment (60 patients)			X	X	X

* Laboratory Tests: FBC, U+Es, LFTs (screening and monitoring). Baseline tests will also include gamma-GT, HbA1C, lipid profile, BNP or NT-proBNP.

*** Pregnancy tests will only be applicable to women of child-bearing potential

8.1. Recruitment

Stroke clinicians and members of the clinical team at each Participation Identification Centre (including research staff associated with the clinical research network) will be asked to recommend potentially eligible patients, including patients who have previously been seen by the clinical service. Research nurses from the clinical research network will screen potential patients for eligibility, discuss the study with them face-to-face if attending for clinical follow-up or send a letter to patients at other times. Eligible patients will be provided invitation letters and the patient information sheet, including the contact details of the OxHARP core team at the Centre for Prevention of Stroke and Dementia, University of Oxford, and invited to contact the core team to discuss the study further. In all centres, patients who have provided specific

consent to be approached for further research studies, either as part of research databases or through previous clinical studies, will be contacted directly by managers of these research databases to invite them to participate in this study using their own materials.

8.2. Screening and Eligibility Assessment

Initial screening against eligibility criteria will be carried out against recorded demographic and clinical information, and then during the screening telephone call / visit. The patient information sheet will be sent to the potential participant prior to the baseline visit, with a minimum 1 week interval prior to the face-to-face assessment. At the screening visit, the study will be explained in detail, and the patient's demographic details and clinical history reviewed, which may include review of their medical notes (if necessary if the participant is unable to be detailed enough, done by secure correspondence with the clinical care team). After informed consent is provided, an ECG, physical exam and laboratory tests will be performed for screening purposes prior to randomisation, except where an ECG is available from the past year, or blood tests (U+Es, FBC) are available from the past 3 months, without a clinical event that would require repeat testing.

8.3. Informed Consent

Informed consent will be taken by the chief investigator, or a delegated study physician, compliant with GCP best practice. The participant must personally sign and date the latest approved version of the Informed Consent form before any study specific procedures are performed. Potential participants from Patient Identification Centres will be asked to contact the OxHARP clinical team and discuss the study first by telephone prior to arranging to visit the John Radcliffe for a formal screening visit.

Written and verbal versions of the Participant Information Sheet and Informed Consent will be presented to the participants detailing no less than: the precise nature of the study; what it will involve for the participant; the implications and constraints of the protocol; the known side effects and any risks involved in taking part. It will be clearly stated that the participant is free to withdraw from the study at any time for any reason without prejudice to future care, without affecting their legal rights and with no obligation to give the reason for withdrawal.

The participant will be allowed as much time as wished to consider the information, and the opportunity to question the Investigator, their GP or other independent parties to decide whether they will participate in the study. Written Informed Consent will then be obtained by means of participant dated signature and dated signature of the person who presented and obtained the Informed Consent. The person who obtained the consent must be suitably qualified and experienced, and have been authorised to do so by the Chief/Principal Investigator. A copy of the signed Informed Consent will be given to the participant. The original signed form will be retained at the study site in the study master file, with a copy in the patient's medical notes.

8.4. Randomisation, blinding and code-breaking

Randomisation will be performed by the Huddersfield PMU at the point of overencapsulation of medication in advance of provision of treatments to the Oxford Clinical Trial pharmacy. Study numbers will then be provided in sequence to participants at the Oxford Clinical Trial pharmacy. Each sequential study ID will be randomly allocated to one of six different treatment schedules, as outlined in the drug allocation

table on page 11, to produce three groups of 12 and three groups of 13 patients. The randomisation schedule will be generated by Huddersfield PMU.

The study will be blinded to the participant, blinded to the core study team ([name], [name], [name]) and blinded to the endpoint assessors (TCD measurement and MRI analysis). In patients consenting to the MRI substudy, the Trials pharmacy (or [name], who is otherwise independent of the study), will identify the visit at which the participant will be taking cilostazol so that the MRI scans can be arranged, but will not inform the patient or core team when sildenafil or placebo are assigned.

If clinical need requires unblinding of a specific patient, this will be done by the study pharmacist who will retain the randomisation schedule, following formal discussion with the Chief Investigator. Due to the low risk level associated with the study medication, and no specific medical intervention indicated for any potential complication that requires prior knowledge of current study treatment, emergency out of hours code-breaking is not required.

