7.3. Exclusion Criteria

- Pregnant or breastfeeding women, women of childbearing age not taking contraception.
 - Acceptable contraception in women of childbearing age is a "highly effective" contraceptive measure as defined by the Clinical Trials Facilitation Group (http://www.hma.eu/fileadmin/dateien/Human_Medicines/01-About_HMA/Working_Groups/CTFG/2014_09_HMA_CTFG_Contraception.pdf) and includes combined (oestrogen and progesterone containing) or progesterone-only contraception associated with inhibition of ovulation, or intrauterine device or bilateral tubal occlusion
- Other major neurological or psychiatric conditions affecting the brain and interfering with the study design (e.g. multiple sclerosis)
- Other causes of stroke such as
 - ≥50% luminal stenosis (NASCET) in large arteries supplying the infarct area

- major-risk cardioembolic source of embolism (permanent or paroxysmal atrial fibrillation, sustained atrial flutter, intracardiac thrombus, prosthetic cardiac valve, atrial myxoma or other cardiac tumours, mitral stenosis, recent (<4 weeks) myocardial infarction, left ventricular ejection fraction less than 30%, valvular vegetations, or infective endocarditis)
 - other specific causes of stroke (e.g. arteritis, dissection, drug misuse)
- Large vessel occlusion on MRA or CTA (carotid, basilar or MCA)
- Modified Rankin Score >3 (requires assistance to walk)
- Unable to swallow
- Renal impairment (eGFR <35ml/min)
- Significant biochemical abnormalities (sodium <130, K+ <2.5 or >5.5, LFTs >3 x upper limit of normal range)
- Life expectancy <2 years
- Contraindication to active agents
 - Concurrent use of alphablocker
 - Regular use of nitrate (ISMN, GTN, other)
 - Heart failure (NYHA 2-4)
 - Severe aortic stenosis
 - Bilateral renal artery stenosis
 - Uncontrolled arrhythmias
 - Previous priapism
 - Anatomical deformation of the penis
 - Recent myocardial infarction (within 6 months)
 - Unstable angina
 - History of non-arteritic ischaemic optic neuropathy
 - Hypotension: BP <90/60
 - Haemodynamically significant aortic / mitral valve disease
 - Sickle cell disease, myeloma, leukaemia
 - Uncontrolled hypertension (BP >180/110 despite treatment with 3 antihypertensives)
- Scheduled elective surgery or other procedures requiring general anaesthesia during the study.

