9. INVESTIGATIONAL MEDICINAL PRODUCT (IMP)

9.1. IMP Description

The principal IMP is oral sildenafil, given at 25mg TDS for one week, then automatically increased to 50mg TDS for a further 2 weeks, if tolerated, as determined by its provision in labelled dispensing packs. If side-effects occur at the higher dose, the dose will be returned to the lower dose. Sildenafil is a phosphodiesterase 5 inhibitor, widely used for erectile dysfunction and used in selected patients with primary pulmonary hypertension.

The comparator will be placebo, also taken three times daily.

The secondary comparator IMP is cilostazol, as a positive control, provided at 50mg bd and titrated to 100mg bd after one week, to continue for 2 further weeks. Cilostazol is a phosphodiesterase 3 inhibitor used at this dose in peripheral arterial disease, and used in large randomised controlled Trials of patients with previous stroke, with a beneficial effect compared to aspirin.¹⁹ It is expected to improve cerebral reactivity²² and pulsatility²⁰ and is included as a positive control to assess whether sildenafil has a similar magnitude of physiological effect, to estimate if a sufficient magnitude of clinical effect would be expected, to justify larger clinical trials. In order to preserve the blinding of this study, whilst taking cilostazol twice a day participants will be given placebo to take at midday. This means that, from the participant's perspective, they are always taking the study medication three times daily.

Participants will start sildenafil and cilostazol at lower doses for a week before being titrated up to the high dose. The high dose is similar to the medication's use in usual care, given more frequently in the case of sildenafil, but the titration is necessary to settle the participants on the new medication.

Medications will be overencapsulated, overlabelled and blinded by the Huddersfield NHS Pharmacy Manufacturing Unit, and dispensed by the Oxford University Clinical Trials pharmacy. Medications will be provided in 'dosette' type packaging providing dosing times, such that throughout the study patients will take TDS medication (sildenafil TDS, placebo TDS, cilostazol – placebo – cilostazol). Code-break will be

provided to and retained by the Oxford University Clinical Trials Pharmacy, with individual code-breaking allowed on request of the CI ([name]) when clinically indicated.

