9.5. Concomitant Medication

All concomitant medications will be listed at each study visit. Concomitant use of other PDE5 inhibitors (sildenafil, vardenafil) or other PDE inhibitors (cilostazol) will not be allowed. Similarly, concomitant use of alpha-blockers, nitrates (GTN, ISMN, nicorandil) or direct vasodilators (hydralazine, naftidofuryl) will not be allowed. Use of anticoagulants or more than one antiplatelet agent will also be contraindicated. If a clinical need for these medications arises, the participant will be withdrawn from the study.

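### Protocol 8.4 dispenses with out-of-hours code-breaking partly on an absolute premise that is not reconciled with 7.3, 9.1, 9.5 or the rest of 8.4

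*Protocol*

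**What the plan says.** Protocol 8.4 sets out one route to unblinding: "If clinical need requires unblinding of a specific patient, this will be done by the study pharmacist who will retain the randomisation schedule", after the case has been formally discussed with the Chief Investigator. It then concludes that "emergency out of hours code-breaking is not required" and gives two reasons. The first is "Due to the low risk level associated with the study medication". The second is that there is "no specific medical intervention indicated for any potential complication that requires prior knowledge of current study treatment".

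Protocol 9.1 places the code-break with the clinical trials pharmacy, with "individual code-breaking allowed on request of the CI" where there is a clinical indication. It states no hours.

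Protocol 7.3 has a list headed "Contraindication to active agents", which includes alpha-blockers and regular nitrates. Anticoagulants and more than one antiplatelet are a separate exclusion, outside that heading.

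Protocol 9.5 says that "concomitant use of alpha-blockers, nitrates (GTN, ISMN, nicorandil) or direct vasodilators (hydralazine, naftidofuryl) will not be allowed" and that "Use of anticoagulants or more than one antiplatelet agent will also be contraindicated". It then provides for the case where a participant comes to need one of these medicines, and the stated consequence is withdrawal from the study.

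The SAP has no code-break procedure. Its section 4.4 says only that unblindings not already foreseen in the protocol will be listed with reasons.

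**The concern.** The second reason in 8.4 is absolute: it covers any complication and any intervention. A provision that limits access to treatment codes should rest on a premise that the rest of the protocol supports, and several sections point the other way.

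The stake is participant safety, not the primary estimate. Everyone enrolled has had a stroke or probable TIA. Each is scheduled for three blinded periods of three weeks, 3 × 3 = 9 weeks of dosing, of which 2 × 3 = 6 weeks are on an active drug. If one of the needs foreseen in 9.5 arises when the pharmacist or Chief Investigator cannot be reached, the protocol gives no route by which the treating team can learn what the participant has been taking.

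**Working it through.** No arithmetic applies. The plan states no figure here, and the point depends on no sample size, variance or error rate. The check is a comparison of sections.

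1. **8.4 against itself and 9.1.** One sentence of 8.4 provides for unblinding when clinical need requires it, and 9.1 does the same on clinical indication. If knowledge of the current treatment could never bear on care, there would be little reason for either provision. The protocol therefore accepts that the need can arise, and nothing in it confines that need to working hours.

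2. **8.4 against 7.3.** The heading in 7.3 ties its list to the active agents. Placebo is not an active agent, so on the protocol's own terms the contraindication for alpha-blockers and regular nitrates turns on whether a participant is taking active drug or placebo. That is information about current treatment.

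3. **8.4 against the drug-specific statements.** Section 4 attributes an antiplatelet effect to cilostazol and does not attribute one to sildenafil. Section 14.7 links a priapism risk to sildenafil. Section 9.1 attributes the omeprazole interaction to cilostazol. None of these says that emergency care depends on allocation. Together they show that the protocol does not regard the three treatments as interchangeable in their risks.

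4. **8.4 against 9.5.** Section 9.5 foresees a need for the prohibited drugs and responds with withdrawal. Withdrawal settles whether the person stays in the trial. It does not tell a treating clinician what was taken that day, and 9.5 does not mention the code-break at all.

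5. **What is left of the rationale.** Without the second reason, the stated basis for 8.4 is the low risk of the medication. That is a separate argument. It sits beside a list of contraindications in 7.3, and 8.4 does not discuss the two together.

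**The case against.** Much of the opposing case stands.

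- **Complication versus concomitant need.** Section 8.4 speaks of interventions for a complication, most naturally one caused by study medication. Sections 7.3 and 9.5 concern other medicines, possibly needed for unrelated reasons. The sections can therefore all be literally true. This is why the point is an unreconciled rationale and not a strict contradiction. The tension inside 8.4, and between 8.4 and 9.1, does not depend on this link.
- **Blanket prohibition.** A reader might infer that 7.3 and 9.5 list acute treatments whose use depends on which drug is being taken. They do not say that. Section 9.5 applies to every participant in every period, so applying it needs no knowledge of allocation. Section 7.3 separates active from placebo, not sildenafil from cilostazol, and its nitrate entry concerns regular use. A specific interaction between one nitrate and one study drug would have to come from outside the documents. However, 9.5 governs trial participation. Once the need has arisen and the person is withdrawn, it no longer guides anyone.
- **Existing provisions.** Section 8.4 says out-of-hours code-breaking is not required, not that it is forbidden, and 9.1 states no hours. Section 10.1 gives participants a telephone number for side effects. Section 7.3 excludes unstable angina, myocardial infarction within 6 months and symptomatic heart failure. These lower the likelihood of an event or soften its consequences. None of them states how a code is obtained when the two named roles are unavailable.
- **Share of the week without cover.** A reader might try to express the gap as a fraction of hours. The documents give no cover hours, and hours without cover do not measure risk in any case.
- **Safety reporting.** A reader might infer that reporting of unexpected serious reactions, or review by the safety board, also needs overnight unblinding. It does not. Protocol 10.6 works to deadlines of 7 and 15 calendar days, and SAP 2.4 concerns unblinding data at the board's request.

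**Conclusion.** The concern holds as a failure to reconcile sections. Section 8.4 rests a participant-safety provision partly on an absolute premise that the protocol's own 7.3, 9.1 and 9.5, and the unblinding sentence in 8.4, do not support. It merits correction because it concerns safety and is cheap to put right, not because a large effect has been shown. No event rate, hours of cover or probability of needing a prohibited drug can be drawn from the documents, so no numerical size is claimed.

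The conclusion rests on three readings: that the heading in 7.3 does not extend to placebo; that the need foreseen in 9.5 may arise suddenly and at any hour, which the protocol neither says nor rules out; and that no other supplied section gives an emergency route. The information sheet and any participant card were not available, so some of the gap may already be covered there.

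**What to change.** Amend protocol 8.4 in three steps:

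1. Remove or correct the sentence stating that no intervention requires knowledge of current treatment.
2. Reconcile 8.4 with 7.3, 9.1 and 9.5, so that the contraindications, the clinical grounds for unblinding and the withdrawal provision are consistent with one another.
3. State how a code-break is obtained when the study pharmacist or Chief Investigator cannot be reached. One example is wider access to the code list the pharmacy already holds. Another is a card carried by the participant that names the possible study drugs and the 9.5 list, if none is already issued.

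Which medicines may be given, and when, is a clinical matter on which nothing is proposed here.

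The cost is amendment wording, some access logistics and possibly a few more individual unblindings. The cost to the analysis should be small: a participant who needs a 9.5 drug is already to be withdrawn, and 8.9 retains data collected up to that point unless consent for this is withdrawn. SAP 4.4 would need a matching edit. It lists only unblindings not foreseen in the protocol, so those made under a newly specified route could otherwise go unlisted.

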8.5. Baseline Assessments

Clinical Assessment

Following assessment of eligibility and full informed consent at the screening visit, the participant will be interviewed for demographic details, medical history, a review of their medical notes (if necessary if the participant is unable to be detailed enough) since screening and undergo a medical examination:

- Vital signs (sitting blood pressure x2 with a BHS validated device, heart rate, oxygen saturations, temperature)
- Cardiovascular examination (heart sounds, postural blood pressure)
- Respiratory examination
- Gastrointestinal examination
- Neurological examination
- National Institute of Health Stroke Scale (NIHSS)
- Modified Rankin Score (mRS)
- Montreal Cognitive Assessment (MoCA)
- Fluid Intelligence and matching pairs cognitive assessments (Biobank protocol)

Clinical Tests

If an ECG within the previous year is not available, or the medical history indicates that a potential cardiac event has occurred since the last ECG, this will be performed prior to randomisation. In addition, if relevant blood tests are not available from the last 3 months, clinical blood tests (~10mls blood) will be performed for FBC, U+Es, LFTs, CRP, BNP or NT-proBNP, gamma-GT, lipid profile, HbA1C. In women of child-bearing potential, a pregnancy test will be performed. These initial clinical tests will be performed for screening according to the inclusion criteria (FBC, U+Es, LFTs), and used for demographic baseline data (CRP, BNP or NT-proBNP, gamma-GT, lipid profile, HbA1C). At each follow-up visit, we will repeat FBC, U+Es, LFTs for monitoring effects of initiating medications.

All patients that have consented to the study will also have twenty millilitres of blood taken at baseline for storage and later analysis. In patients this will be drawn, where possible, at the same time as the screening visit bloods. Serum, plasma, buffy coat and whole blood samples are prepared and transferred to cryotubes. Each cryotube is labelled with a unique identification number, recorded in the specimen logbook and frozen at -85°C . All blood samples are stored in freezers in laboratories in the Wolfson Centre for Prevention of Stroke and Dementia for up to 2 years after final recruitment to the study, to allow for analysis of the samples. Samples will be tested for biomarkers that predict response to the randomized treatment allocation in the study, and for correlation with severity of baseline white matter hyperintensities (to determine interaction with treatment effect). Blood will be stored and then analysed at completion of the study, as the extent of testing will depend upon the demonstrated effect of medications in the study, whilst allowing for assessment of new biochemical and genetic markers reported during the study, in this rapidly developing field. As a minimum, markers of endothelial function (ICAM, VEGF, vWF) and genetic targets of the medications in the trial, shown to be associated with small vessel disease (ie PDE3 polymorphisms), will be measured. These will not specifically include tests of direct clinical relevance to the participant and are very unlikely to have clinical implications. In the unlikely circumstance that incidental biomarker or genetic results that could be relevant to the participant are identified, these will be assessed by an independent physician ([name]), the participant informed and a referral made to an appropriate specialty, where clinically indicated.

Physiological Assessment

Central Aortic Blood Pressure / Aortic Pulse Wave Velocity (10 minutes)

Radial artery pulse waveforms will be recorded using a pressure tonometer and designated software (SphygmoCor, At-Cor Medical, Sydney, Australia). Briefly, mean values of approximately 10 radial pulse waves will be used to generate a corresponding central aortic pressure waveform with a validated mathematical transfer function. A minimum of 10 radial artery pulse waveforms are required by the software to calculate the AI_x and to also derive an operator index (indicating the quality and reproducibility of the arterial signal (SphygmoCor, At-Cor Medical, Sydney, Australia).

Aortic arterial stiffness will be assessed by the gold standard technique of carotid-femoral pulse wave velocity. This requires recording of the pulse wave by applanation tonometry with the SphygmoCor device from both carotid and femoral arteries, and the speed of transmission between the two sites used to estimate the velocity of the pulse wave. This provides a measure of the stiffness of the central arteries.

Transcranial Doppler Ultrasound (TCD)

TCD will be performed with DiaMon 2MHz probes, firstly with a handheld probe to best identify the middle cerebral and basilar arteries, with application of ultrasound gel over the temporal (in front of the ear) and suboccipital windows (at the nape of the neck). The M1 segment will be identified between 45-55mm depth as the segment of the artery with blood flow towards the probe, slightly superficial to a site of bifurcation into another vessel with flow away from the probe (the anterior cerebral artery), with blood flow towards the probe ideally extending for at least 1cm within the skull. The basilar artery will be identified via the trans-foramen magnum bone window, identifying blood flowing away from the probe at $>75\text{mm}$. The maximal velocity in these segments will be identified and peak, trough and mean blood flow velocities will be derived from the wave form envelope, taking the average of at least 5 cardiac cycles. From these measures Gosling's pulsatility index will be derived as the primary measure of cerebral pulsatility. Where bone windows are adequate (ie MCA blood flow can be insonated via the temporal bone), bilateral

monitoring insonation of the middle cerebral artery will be established with 2 probes held to the head a with a comfortable headset, with spectra acquired by a DWL Doppler Box to a dedicated laptop. This waveform will be acquired over 10 minutes with concurrent heart rate and blood pressure monitoring (see below). End-tidal carbon dioxide monitoring will be performed with AD Instruments Gas Analyser ML206. All waveforms will be simultaneously acquired with a AD Instruments Powerlab 8/35.

Continuous non-invasive blood pressure monitoring

Continuous ECG and BP will be recorded using a Finometer (BP monitor which allows continuous non-invasive assessment of finger arterial pressure). After a period of at least 5 minutes of rest and after achievement of a satisfactory BP signal from the monitor and the stabilization of BP at the same level, recordings will be performed for up to 10 minutes (minimum 5 minutes). The outputs from the Finometer and simultaneous surface ECG recordings will be analysed to estimate cerebral autoregulation and transmission of arterial pulsatility using in-house analysis programs written in Matlab, according to both sequential and spectral methods. The system will be allowed to establish a stable internal calibration before this function is turned off for the monitoring period. A standard brachial blood pressure will be obtained twice with a calibrated device (A&D UA-767 BT) from the contralateral arm twice, and the Finometer trace calibrated to this reading by 2 point calibration.

Cerebral Autoregulation (10 minutes)

Once established, bilateral TCD, blood pressure, ECG and end-tidal CO₂ will be acquired simultaneously for 5 minutes after a minimum of 5 minutes of supine rest. Continuous systolic, diastolic and mean values will be derived and related to each other by transfer function analysis using in-house software written in Matlab. This allows estimation of baroreceptor sensitivity and cerebral autoregulation.

CO₂ reactivity (10 minutes)

Following the period of monitoring, reactivity to CO₂ will be assessed by 3 minutes of inhalation of 6% CO₂, delivered via a respiratory circuit with a non-invasive ventilation mask and harness, supplied with 2 alternating periods of medical air versus 6%CO₂/21%O₂/balance N₂. The resulting increase in MCA mean flow velocity on TCD will be related to the change in end-tidal CO₂ to determine the vasodilatory response, adjusted for any change in blood pressure. Secondly, the participant will be instructed to hyperventilate at 1 breath per second for 30 seconds to reduce etCO₂ and estimate change in mean flow velocity per unit change in etCO₂.

Peripheral Vascular Reactivity (10 minutes)

Effects of medication on peripheral endothelial function will be estimated by assessment of flow-mediated slowing (Vicorder, Skidmore Industries). This determines the change in speed of flow of the pressure waveform between two sites in the arm, before and after a short period of occlusion. This induces endothelium dependent vasodilatation, which results in slowing of the speed of blood flow. If the previous tests last >60 minutes to achieve accurate measurements, or if the participant finds this procedure too uncomfortable this element may be omitted at follow up visits.

Blood pressure monitoring

Patients will be provided with a home blood pressure monitor to record their blood pressure twice daily (on waking and evening), recorded three times at each sitting, for 7 days prior to their subsequent study visit (A&D UA-767 BT). Patients will be asked to record their blood pressure readings and return them for

assessment of how allocated treatment affects blood pressure, and how this may interact with the primary outcome measure. If potential symptoms of hypotension occur, patients may be requested to perform additional readings for clinical safety purposes. Participants will be asked to record any side-effects on the same diary card as used for blood pressure monitoring.

Medication Dispensation

Study medication / placebo will be dispensed by the Oxford University Clinical Trials Pharmacy after randomisation.

